1.2 DRUG PROFILE

In addition, the GLYT1

inhibitor prototype sarcosine has shown to improve positive, negative, and cognitive symptoms in patients with schizophrenia (R13-4447; R13-4524). It is therefore thought that treatment with BI 425809 has the potential to improve cognitive functioning in patients with schizophrenia.

In a proof of clinical concept trial of another GLYT1 inhibitor, bitopertin, efficacy signals were observed in negative symptoms of schizophrenia (R13-4509), but not replicated in phase III trials (R14-4313; R15-1273).

Page 18 of 116

Proprietary confidential information © 2019 Boehringer Ingelheim International GmbH or one or more of its affiliated companies

The safety observations from clinical trials have replicated findings from other compounds with the same mode of action (R13-4450; R13-4451; R13-4508). Potential risks associated with BI 425809 are transient visual disturbances, and somnolence. Based on class-effect, BI 425809 may have the potential to be associated with hemoglobin decrease (R15-1266; R15-1273; R15-1270).

Page 19 of 116

Page 20 of 116

Proprietary confidential information © 2019 Boehringer Ingelheim International GmbH or one or more of its affiliated companies

Clinical experience in humans

At the time of preparation of this clinical trial protocol, BI 425809 has been used in seven phase I trials:

- 1346.1 Single rising dose (SRD) trial: completed, report archived
- 1346.2 Multiple rising dose (MRD) trial: completed, preliminary data available
- 1346.3 Proof of mechanism trial: completed, report archived
- 1346.4 Single rising dose (SRD) in Japanese and Chinese trial: completed, preliminary data available
- 1346.10 Itraconazole-interaction trial: completed, report archived
- 1346.22 interaction with cytochrome P450 and P-glycoprotein substrates trial: completed, report archived
- 1346.18 DDI strong CYP3A4 inducer, completed

For a more detailed description of the drug profile refer to the current Investigator's Brochure (IB) which is included in the Investigator Site File (ISF).

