2.3 BENEFIT - RISK ASSESSMENT

The overall safety profile of BI 425809 is outlined in the current IB c02156531 Drug-related risks and safety measures

Considering the chronic and severe disease burden of CIAS, the potential therapeutic benefits are assessed to outweigh the currently understood potential risks of the treatment.

Based on non-clinical toxicology data, clinical data from other compounds in the same class, and subjects exposed in phase I trials, BI 425809 is assessed to be generally safe and welltolerated. Most common AEs were CNS related, headache being the most frequent. There is potential for BI 425809 to be associated with transient visual disturbances, and somnolence. These effects are understood to be mostly mild to moderate and transient.

Decreased hemoglobin is also considered to be a potential risk based on preclinical data and class effect; however, no clear decrease in hemoglobin was seen in BI 425809-treated subjects compared to placebo in phase I trials so far (of up to 14 days duration). Patients with hemoglobin less than 120 g/L (12g/dL) in men or 115g/L (11.5g/dL) in women will be excluded from participation.

Administration with strong CYP3A inhibitor/ inducers did significantly impact the total exposure of BI 425809. As BI 425809 is a sensitive substrate of CYP3A4, co-administration of moderate to strong CYP3A4 inhibitors and inducers are excluded during the participation in this trial. Furthermore, as data of the DDI cocktail study 1346.22 suggest that BI 425809 is a mild CYP3A4 inducer, clinical monitoring is considered necessary when co-administering sensitive substrates of CYP3A4 at least to the highest tested dose of 25 mg BI 425809. Sensitive CYP3A4 substrates with a narrow therapeutic index are excluded during this trial.

Regarding the potential risk while operating machinery, please refer to Section 4.2.2.2.

Consistent with the FDA draft guidance entitled "Suicidal Ideation and Behavior: Prospective Assessment of Occurrence in Clinical Trials", prospective assessment of suicidal ideation and behavior is included in this study using the C-SSRS.

Although rare, a potential for drug-induced liver injury is under constant surveillance by sponsors and regulators. Therefore, this trial requires timely detection, evaluation, and follow-up of laboratory alterations in selected liver laboratory parameters to ensure patients' safety, see also Section 5.3.6.1.

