3.2 DISCUSSION OF TRIAL DESIGN, INCLUDING THE CHOICE OF CONTROL GROUP(S)

A parallel group design was chosen for this trial to detect the effects of BI 425809 compared to placebo on cognition in patients with schizophrenia on stable antipsychotic treatment. The primary analysis of efficacy is planned for 12 weeks of treatment. The 1 and 4 weeks post-treatment follow-up visits is considered to be sufficient to evaluate the pharmacodynamic effect of BI 425809 after discontinuation, to capture withdrawal effects and allow for assessment of reversibility of any unexpected side-effects.

Boehringer Ingelheim		28 Mar 2019
BI Trial No.: 1346.9		
Doc. No.: c03559983-04	Trial Protocol	Page 26 of 116

Proof of clinical concept and dose finding are combined within this single phase II trial. In order to achieve both aims in an efficient way, i.e., with a comparably large success probability, the generalized MCPMod approach (R10-1424) has been implemented as the statistical design. This approach is able to incorporate potential relationships between the different doses into the evaluations via optimal test contrasts which increases the probability of success compared with clinical multiple comparison procedures. MCPMod has been evaluated by the EMA recently and is considered to be an efficient statistical methodology for model-based design and analysis of phase II dose finding studies under model uncertainty (EMA qualification opinion). As a second step for designing the trial efficiently the allocation ratio has been chosen to be 1:1:1:1:2 for the treatment groups compared with the placebo. Thereby the success probability of the trial is increased further compared to a balanced allocation ratio whilst keeping the risk of a false positive outcome at the same level. A sufficiently broad set of candidate shapes for the dose-response relationship has been chosen including monotonic and non-monotonic options. Details of the statistical approach including the set of candidate models as well as a sample size justification are given in Section 7.

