- 15) Any suicidal ideation of type 4 or 5 in the Columbia Suicidal Severity Rating Scale (C-SSRS) in the past 3 months (i.e. active suicidal thought with intent but without specific plan, or active suicidal thought with plan and intent) prior to randomization
- 16) In the judgment of the investigator any clinically significant finding of the physical examination (including BP, PR and ECG) or laboratory value (as measured by the central laboratory at visit 1) that would jeopardize the patient's safety while participating in the trial and their capability to participate
- 17) Any symptomatic/unstable/ uncontrolled or clinically relevant concomitant disease or any other clinical condition that would jeopardize the patient's safety while participating in the trial and capability to participate in the trial as per investigator's opinion.
- 18) Severe renal impairment defined as an eGFR < 30mL/min/1.73m² in the screening central lab report

- 19) Indication of liver disease, defined by serum levels of either ALT (SGPT), AST (SGOT), or alkaline phosphatase above 3 times upper limit of normal (ULN) as determined in the screening central lab report
- 20) Known history of HIV infectionand/or a positive result for ongoing Hepatitis B or C infection on the Visit 1 central lab report
- 21) Medical history of primary or recurrent malignant disease with the exception of resected cutaneous squamous cell carcinoma in situ, basal cell carcinoma, cervical carcinoma in situ or in situ prostate cancer with a normal prostate specific antigen (PSA) post treatment
- 22) Significant or unstable physical condition that in the investigator's judgement may require change in medication or hospitalisation that would impact cognitive function, or planned elective surgery requiring general anesthesia during the study period
- 23) Hemoglobin less than 120 g/L (12g/dL) in men or 115 g/L (11.5g/dL) in women
- 24) History of hemoglobinopathy such as thalassemia major or sickle-cell anemia
- 25) Women who are pregnant, nursing, or who plan to become pregnant while in the trial orMen who are able to father a child, unwilling to be abstinent or use adequate

Men who are able to father a child, unwilling to be abstinent or use adequate contraception for the duration of study participation and for at least 28 days after treatment has ended

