5.3.3 Safety laboratory parameters

The laboratory tests listed in Table 5.3.3: 1 will be performed at the central laboratory service provider. Patients do not have to be fasted for the blood sampling for the safety laboratory. Instructions on collection, handling/ processing, and shipping of the samples will be provided in the investigator site file by the central laboratory. For time points of laboratory sampling refer to the Flow Chart.

Laboratory results of the patients will be available to the respective investigator and to the BI Clinical Monitor of each country (central laboratory website), and selected abnormal laboratory alerts will be sent automatically to the sites and to the sponsor within 24 hours.

Laboratory values that are out of range should be commented on lab report print-outs and evaluated by the investigator for clinical significance. Clinically relevant abnormal laboratory test results must be confirmed using an unscheduled visit lab kit and should be repeated until normalization or stabilization or until an alternative explanation has been found.

Clinically significant abnormal laboratory results should be reported by the investigators in eCRF either on baseline condition (from V1 test) or on adverse event page (from subsequent visits test).

The following lab parameters will not be determined at each study visit:

- TSH at screening only
- Vitamin B12 and folate at screening only

Page 49 of 116

Proprietary confidential information © 2019 Boehringer Ingelheim International GmbH or one or more of its affiliated companies

Category	Test name
Haematology	Hematocrit (Hct) Hemoglobin (Hb) (for patients with >2g/dL decrease in hemoglobin since baseline, the following tests will be added: serum ferritin, serum iron, TIBC, reticulocyte index) Red Blood Cell Count/ Erythrocytes Reticulocyte Count White Blood Cells / Leukocytes Platelet Count/ Thrombocytes MCV, MCH, RDW, MCHC
	Diff. Automatic (manual if diff. automatic is abnormal) - Neutrophils - Eosinophils - Basophils - Monocytes - Lymphocytes
Chemistry	AST(GOT) ALT(GPT) Alkaline Phosphatase (AP) Creatine Kinase (CK) CK-MB, only if CK is elevated Gamma-Glutamyl Transferase (GGT/γ-GT) Lactic Dehydrogenase (LDH) Lipase
Chemistry	Amylase Calcium Sodium Urea (BUN) Potassium Glucose Creatinine Vitamine B12 Bilirubin Total, fractionated if increased Protein, Total C-Reactive Protein Cholesterol, total Triglycerides TSH Folate eGFR

Table 5.3.3: 1 Safety laboratory tests

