7.3.4 Safety analyses

Adverse events will be coded using the Medical Dictionary for Regulatory Activities (MedDRA) coding dictionary. Standard BI summary tables and listings will be produced. All adverse events with an onset between the start of treatment and the end of the residual effect period (REP), a period of 11 days after the last dose of trial medication, will be assigned to the treatment period for evaluation.

All treated patients will be included in the safety analysis and will be summarized under the actual trial medication received at randomization. In general, safety analyses will be descriptive in nature and will be based on BI standards. No hypothesis testing is planned.

Statistical analysis and reporting of adverse events will concentrate on treatment-emergent adverse events. To this end, all adverse events occurring between the start of treatment and the end of the residual effect period will be considered 'treatment-emergent'. The residual effect period is defined as 11 days after the last dose of trial medication. Adverse events that start before first drug intake and deteriorate under treatment will also be considered as 'treatment-emergent'.

Frequency, severity, and causal relationship of adverse events will be tabulated by system organ class and preferred term after coding according to the current version of the MedDRA. Frequency tables for all adverse events, protocol-specified adverse event of special interest (AESI), serious adverse event (SAE), adverse event leading to death, adverse event leading to discontinuation, investigator assessed drug-related adverse event and serious adverse event will be generated for treatment-emergent adverse events. In addition, summary statistics and descriptive analyses will be conducted for other safety parameters including worsening of disease state as assessed by PANSS and suicidality as assessed by C-SSRS.

Laboratory data will be analysed both quantitatively as well as qualitatively. The latter will be done via comparison of laboratory data to their reference ranges. Values outside the reference range as well as values defined as clinically relevant will be highlighted in the listings. Treatment groups will be compared descriptively with regard to distribution parameters as well as with regard to frequency and percentage of patients with abnormal values or clinically relevant abnormal values.

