#### 7.8.2 Laboratory data

The analyses of laboratory data will be descriptive in nature and will follow (10).

Descriptive statistics for laboratory values will be displayed using the converted values. Shift tables of change in laboratory measurements between baseline and worst value on treatment, between baseline and last value on treatment, and between worst and last value on treatment will also be presented.

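### SAP 7.8.2 plans no count by arm of patients whose hemoglobin falls more than 2 g/dL, and no specific summary of recovery at Follow-up 2

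*SAP*

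**What the plan says.** Protocol 1.2 says that "BI 425809 may have the potential to be associated with hemoglobin decrease". Protocol 2.3 repeats it: "Decreased hemoglobin is also considered to be a potential risk based on preclinical data and class effect". It adds that phase I, with dosing of up to 14 days, showed no clear decrease against placebo.

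The protocol gives hemoglobin special handling. Exclusion criterion 23 sets an entry floor: "Hemoglobin less than 120 g/L (12g/dL) in men or 115 g/L (11.5g/dL) in women". Table 5.3.3: 1 sets a within-patient trigger: "for patients with >2g/dL decrease in hemoglobin since baseline, the following tests will be added". The Flow Chart schedules safety laboratory tests at Visits 1, 2 and 4, at (e)EOT and at Follow-up 2.

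For analysis, protocol 7.3.4 plans quantitative and qualitative evaluation of laboratory data. Of the qualitative part it says: "The latter will be done via comparison of laboratory data to their reference ranges". It also compares arms on how many patients have abnormal or clinically relevant abnormal values.

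SAP 7.8.2 plans descriptive statistics of laboratory values and shift tables: "Shift tables of change in laboratory measurements between baseline and worst value on treatment, between baseline and last value on treatment", plus one from worst to last value on treatment. It defers to an internal guide (reference 10), which is not available. The section does not mention hemoglobin and does not define the shift categories.

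**The concern.** The trial doses for 12 weeks and is meant to support a dose choice on efficacy and safety. For a risk named in advance, the useful patient-level question is how many patients in each arm had a substantial fall and whether they recovered. The protocol already has a yardstick for a substantial fall, but neither document turns it into a count.

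A reference-range shift table answers a different question, and it can lose falls at both ends:

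- A patient who starts well above the lower limit can lose more than 2 g/dL and still read normal to normal.
- A patient who is eligible but already below the laboratory's lower limit reads low to low however far hemoglobin drops.

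All three shift tables stop at the end of the on-treatment window, and no recovery summary is specified. At stake is a blurred picture by dose of one safety signal. The efficacy analysis is not affected.

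**Working it through.** The plan states no figure to reproduce. There are two checks.

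**1. Timing of Follow-up 2**

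- The last dose is taken the day before EOT (protocol 4.1.4).
- On-treatment stops at last dose + residual effect period + 1 day (SAP Table 6.1: 2), which is 11 + 1 = 12 days after the last dose.
- Follow-up 2 is EOT + 21 to EOT + 35 days (SAP Table 6.7: 1), which is 21 + 1 = 22 to 35 + 1 = 36 days after the last dose.

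Since 22 > 12, an in-window Follow-up 2 sample cannot enter a table of on-treatment values. Follow-up 1 has no scheduled safety laboratory tests, so Follow-up 2 is the only scheduled hemoglobin after EOT.

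**2. How often a fall above 2 g/dL shows no shift**

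The documents supply only the entry floors *f*: 12.0 g/dL for men and 11.5 for women. The rest is assumed:

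- laboratory lower limit *L*: 13.0, 13.5 or 14.0 (men); 11.5 or 12.0 (women)
- baseline mean: 14.5 or 15.0 (men); 13.0 or 13.5 (women)
- baseline normal with SD 1.0, truncated at *f*
- 65% men
- shift categories equal to the reference range

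For a fall of *d*, with *B* the untruncated baseline:

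no-shift share = [P(B ≥ L + d) + P(f ≤ B < L)] / P(B ≥ f)

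The first term is normal to normal and the second is low to low.

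Mid-range example, d = 2.1:

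- Men (mean 15.0, L = 13.5): P(B ≥ 15.6) = 0.274; P(12 ≤ B < 13.5) = 0.0655; P(B ≥ 12) = 0.9987. Share = 0.340.
- Women (mean 13.5, L = 12.0): P(B ≥ 14.1) = 0.274; P(11.5 ≤ B < 12) = 0.044; P(B ≥ 11.5) = 0.977. Share = 0.326.
- Combined: 0.65 × 0.340 + 0.35 × 0.326 = 0.335.

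Over all combinations:

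| Fall (g/dL) | No shift, both kinds | Normal to normal only | Mid-range, both kinds |
|---|---|---|---|
| 2.1 | 27-48% | 9-46% | 34% |
| 2.5 | 20-33% | 4-31% | 22% |
| 3.0 | 11-26% | 1-16% | 13% |

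A second set of assumptions used falls spread evenly over 2-3 g/dL, SD 0.9-1.1, means up to 15.5 (men) and 14.0 (women), and female limits up to 12.5. It gives about 15-50% with both kinds counted (18-27% in its central cases). Among patients with a normal baseline it gives about 2-50%.

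Individual illustrations, taking L = 13.0: a man going from 15.5 to 13.4 g/dL loses 2.1 and reads normal to normal. A man going from 12.5 to 10.4 loses 2.1 and reads low to low, although he met the entry floor.

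**Scale within one arm of 84.** Suppose 8 patients fall by 2.1-2.5 g/dL. With a no-shift share of 20-48%, the shift table shows 8 × 0.52 = 4.2 to 8 × 0.80 = 6.4 of them, so about 4-6. If nobody else changes, the arm mean moves by 8 × 2.1 / 84 = 0.20 to 8 × 2.5 / 84 = 0.24 g/dL.

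**The case against.** A reader might infer that hemoglobin is read only through shift tables. It is not. The same SAP section plans descriptive statistics, and protocol 7.3.4 plans counts by arm of abnormal and clinically relevant abnormal values. Clinically relevant laboratory changes are also recorded as adverse events, and SAP 7.8.1 lists marked haematological abnormalities among other significant events. This stands. However, those counts use reference ranges, limits not stated in the documents, or clinical judgement. None counts patients by size of fall, and a mean dilutes a few large falls.

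A reader might also infer that the Follow-up 2 sample is unused. The documents do not support that. The descriptive statistics carry no on-treatment restriction, protocol 7.3.4 covers safety data at the end-of-trial evaluation, and the SAP has a table of follow-up adverse events. What remains is that Follow-up 2 is outside the shift tables and no recovery summary is named. Protocol 3.2 does say the follow-up visits "allow for assessment of reversibility of any unexpected side-effects", but that concerns unexpected effects and hemoglobin decrease was anticipated, so it is not a promise about hemoglobin.

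Three further points stand:

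- The 2 g/dL figure triggers laboratory tests and is not defined as an analysis threshold.
- Hemoglobin decrease is a potential risk, not an established harm of this drug.
- The internal laboratory guide may define the shift categories, or may already require these displays. It cannot be checked.

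Finally, it cannot be claimed that most such falls, or any fixed share of them, would be missed. The percentages rest on assumed limits and baselines. Low-to-low pairs arise only if the laboratory limit lies above the entry floor, and without them the share runs from about 1% to 46%.

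**Conclusion.** The point holds as a gap in specification. Neither document plans a count by arm of patients with a hemoglobin fall above the protocol's own 2 g/dL trigger. By date arithmetic, Follow-up 2 hemoglobin cannot enter any of the three shift tables, and no recovery summary is specified.

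The timing result rests only on figures in the documents. The no-shift share, roughly 10-50% depending on the size of the fall, is conditional on reference-range categories and on the assumed limits and baselines. It shows that the loss could matter, not how large it will be. This is a worthwhile, inexpensive improvement to the safety reporting and does not mean that hemoglobin goes unanalysed.

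**What to change.** Add to SAP 7.8.2, by treatment arm in the treated set:

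1. The number and percentage of patients with a hemoglobin decrease of more than 2 g/dL from baseline at any on-treatment time.
2. Descriptive change from baseline in hemoglobin at Week 6, Week 12 and Follow-up 2.
3. For patients flagged in (1), the Follow-up 2 value relative to baseline, with the number who have no Follow-up 2 sample.

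Keep the shift tables and state which categories they use. If the internal laboratory guide already requires any of this, one sentence in the SAP saying so is enough for that part. Confidence intervals for active against placebo, or a split by sex, are optional extras; the safety plan is descriptive and the point does not depend on them.

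The cost is SAP wording and a small amount of extra descriptive output from central laboratory data already scheduled. No test is added. The trigger in protocol Table 5.3.3: 1 is used only for counting, so no clinical rule changes.

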#### 7.8.3 Vital signs

Only descriptive statistics are planned for this section of the report.

#### 7.8.4 ECG

Clinical relevant abnormal ECG findings will be reported and analysed as AEs.

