5.3.4 Electrocardiogram

The 12-lead ECGs will be performed as scheduled in the Flow Chart. Twelve-lead ECGs (I, II, III, aVR, aVL, aVF, V1 - V6) will be recorded using equipment provided by a central ECG vendor. The ECGs will be recorded for at least 10 second duration after the subjects have rested for at least 5 minutes in a supine position. Electrode placement will be performed according to the method of Einthoven/Goldberger (ankles and wrists). At all time points indicated in the Flow Chart, single ECGs will be recorded. ECG recordings at planned time points may be repeated for quality reasons like alternating current artefacts, muscle movements and electrode dislocation. In this case the repeated ECG recordings will be used if quality was better.

The investigator or a designee will evaluate whether the ECG is normal or abnormal and whether it is clinically significant, if abnormal. The electronic version of the ECG is regarded as source data. Dated and signed printouts will be stored in the patient's medical file if there is no validated and certified e-medical record for ECG data.

Additional ECGs may be collected by the investigator for safety reasons. Clinically relevant findings noticed at baseline assessment should be reported as baseline condition. Clinically relevant abnormal findings noticed after baseline assessment will be reported as adverse events and followed up and/or treated locally until normal or stable condition.

All ECGs will be transmitted electronically to the central ECG vendor in order to enable a centralized and independent re-evaluation of all 12-lead ECGs. A centralized and independent re-evaluation will be done. Abnormalities detected during this centralized ECG evaluation will not necessarily qualify as AE.

Central evaluation on individual ECG level will be performed by the vendor and a report will be provided to the site. Decisions on eligibility for the trial and treatment or further follow-up of any findings are in the responsibility of the investigator.

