Vital signs, physical examinations, or other safety-relevant data observed at screening, baseline, during the course of the trial and at the end-of-trial evaluation will be assessed with regard to possible changes compared to findings before start of treatment.

Page 70 of 116

Proprietary confidential information © 2019 Boehringer Ingelheim International GmbH or one or more of its affiliated companies

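### SAP Section 7.8.4 analyses ECGs only as AEs, so centrally read abnormalities that the site does not call clinically relevant appear in no visible planned summary

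*SAP*

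**What the plan says.** SAP Section 7.8.4 reads, in full: "Clinical relevant abnormal ECG findings will be reported and analysed as AEs".

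Protocol Section 5.3.4 describes two readings of each ECG. The first is at the site: "The investigator or a designee will evaluate whether the ECG is normal or abnormal and whether it is clinically significant, if abnormal". From there, "Clinically relevant abnormal findings noticed after baseline assessment will be reported as adverse events". The second is central: "All ECGs will be transmitted electronically to the central ECG vendor in order to enable a centralized and independent re-evaluation of all 12-lead ECGs". The vendor's report on each ECG goes back to the site, and decisions on follow-up stay with the investigator. On the central reading the protocol adds: "Abnormalities detected during this centralized ECG evaluation will not necessarily qualify as AE".

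Protocol Section 7.3.4 says of safety data in general: "All treated patients will be included in the safety analysis and will be summarized under the actual trial medication received at randomization". Its last paragraph begins "Vital signs, physical examinations, or other safety-relevant data observed at screening, baseline" and goes on to cover data during the trial and at its end. All of these "will be assessed with regard to possible changes compared to findings before start of treatment". Section 5.7 gives the purpose of the scheduled measurements as showing changes caused by the drug, and lists ECG with physical examination, vital signs and laboratory values.

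SAP Section 4, which lists changes to the planned analysis, deals only with the wording of the SCoRS endpoint.

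**The concern.** The central reading is the only ECG assessment in the trial made independently of the site. Under the SAP it counts only when the investigator turns a finding into an AE. The AE tables are therefore filtered by many separate site judgements of clinical relevance, and what that filter removes is not shown anywhere.

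The trial is meant to identify doses for phase III on safety as well as efficacy. A pattern of centrally read abnormalities that rises with dose, each one minor enough that the site does not call it relevant, would not show in an AE count. The report could then state that there was no ECG signal without having tabulated the readings collected to look for one.

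**Working it through.** No figure in the plan needs to be reproduced. The check compares sections and counts the ECGs affected.

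**1. Where each ECG result ends up (Protocol 5.3.4; SAP 7.8.1 and 7.8.4)**

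| Site judgement after baseline | Central reading | Visible planned output |
|---|---|---|
| Clinically relevant | Normal or abnormal | AE tables, by arm |
| Not clinically relevant | Abnormal | None |
| Not clinically relevant | Normal | None |

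The second row is the gap. Because the third row has no output either, the number of ECGs read centrally in each arm, which would be the denominator, is not reported.

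**2. How other safety data are handled**

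- Laboratory data (SAP 7.8.2): descriptive statistics, plus shift tables from baseline to worst value, baseline to last value, and worst to last value on treatment.
- Vital signs (SAP 7.8.3): descriptive statistics.
- ECG (SAP 7.8.4): AEs only.

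**3. What the protocol asks for**

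Section 7.3.4 names vital signs and physical examinations, then adds a general class of other data relevant to safety. ECG falls in that class by a reasonable reading: Section 5.3.4 sits under the heading for assessment of safety, and Section 5.7 names ECG among the changes to be seen. The explicit sentence on comparing treatment groups descriptively is in the laboratory paragraph. For ECG the by-arm element rests only on the general rule that safety data are summarised by treatment received, so the ground for change from pre-treatment findings is the firmer of the two.

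**4. How many ECGs are affected**

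The flow chart schedules ECGs at Visits 1, 2 and 4, at (e)EOT and at Follow-up 2. Planned numbers are 84 per active arm and 168 on placebo, 504 in total.

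- On treatment (Visit 4 and EOT): 2 × 504 = 1,008, made up of 2 × 84 = 168 in each active arm and 2 × 168 = 336 on placebo (4 × 168 + 336 = 1,008).
- Follow-up 2: 1 × 504 = 504.
- The 1,008 is before dropout. If only the 450 evaluable patients in Table 7.7: 1 contributed both ECGs, it would be 2 × 450 = 900. The true loss should be smaller, because patients who stop early are asked to attend an eEOT visit.

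**5. Why Follow-up 2 is counted separately**

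The residual effect period is 11 days after the last dose. Follow-up 2 is due 28 days after EOT with a window of 7 days either way, so at the earliest 28 − 7 = 21 days after EOT. That is later than 11 days, so these ECGs are post-treatment. For completers, Protocol Section 4.1.4 puts the last dose on the day before EOT, so the EOT ECG falls inside the 11 days.

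**The case against.** The strongest reply is that the SAP does what the protocol asks. The secondary safety endpoint in Protocol Section 5.1.2 is the percentage of patients with (S)AEs, with clinically relevant ECG abnormalities included. Section 5.3.7 likewise records ECG changes as AEs when the investigator judges them clinically relevant. This stands: the AE rule is consistent with the protocol and should stay.

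It can also be said that the central reading is there to support care of the individual patient, since the report goes to the site. This stands in part. Central findings can reach the AE tables through the investigator, and only those judged not relevant are left out. But the protocol describes the central reading as independent, and nothing in it limits that reading to site support.

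Three stronger readings are tempting, and the documents do not support them.

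- A reader might infer that ECGs are never compared with baseline or between arms. Clinically relevant findings at baseline are recorded as baseline conditions, later ones become AEs, and AEs are tabulated by arm. That is a comparison at patient level, although a filtered one.
- A reader might infer that the SAP flatly breaches Protocol Section 7.3.4. That section does not name ECG and prescribes no means, change scores or shift tables.
- A reader might want to state how precisely a shift in ECG intervals could be estimated. Neither released document names an ECG interval or says that the vendor supplies numeric values, so any such figure would describe data that may not exist.

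Finally, the released SAP has redactions, and Protocol Section 7.3.4 refers to sponsor standards that are not available here, so an ECG summary planned elsewhere cannot be excluded. Against that, Section 7.8.4 shows no gap, the visible contents list no other ECG analysis, and the SAP's references include guides for AE and laboratory data but none for ECG.

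**Conclusion.** The point holds as a gap in completeness. As the visible SAP stands, central ECG abnormalities that the site does not call clinically relevant have no planned summary, although every ECG is read centrally and comparable safety data are summarised. About 1,008 on-treatment ECGs are affected (900 if only the evaluable number contributed), plus 504 at Follow-up 2. How many of them would show an abnormality that stays out of the AE tables cannot be worked out from the documents.

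The conclusion rests on two assumptions: that ECG belongs to the general class of safety data in Protocol Section 7.3.4, and that no ECG summary is hidden by redaction. It does not touch the primary analysis. It is worth acting on because the readings are already being made and the trial is meant to inform dose choice on safety.

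**What to change.** Keep the sentence in SAP Section 7.8.4 and add a descriptive summary of the central ECG evaluation on the treated set, by arm:

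- a shift table from the Visit 2 result (normal or abnormal) to the worst on-treatment result, with the number of patients evaluated;
- the Follow-up 2 results shown separately as post-treatment;
- only if the vendor delivers numeric values, descriptive statistics for value and change from Visit 2 by visit.

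State what is done when the Visit 2 ECG is missing, because SAP Section 6.7 mentions the fallback to screening only for PANSS and eC-SSRS. Record the addition in SAP Section 4. If the central reading was intended only to support the sites, say so there and give the reason.

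The cost is one or two extra descriptive tables and possibly a data transfer from the vendor. No new assessments and no hypothesis tests are needed.
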